## **METHODS**

**Study design:** We propose to conduct a pilot non-randomized-controlled trial to evaluate the impact of “Tomando control de su salud”, an evidenced-based intervention for chronic disease self-management, in the quality of life of patients living with Long-COVID in Puerto Rico.

**Participant selection:** We will invite patients from our cohort study during the 12-month follow-up call. All participants identified with conditions associated with Long COVID or chronic diseases will be invited to participate. These are the inclusion and exclusion criteria:

Inclusion criteria:

- 1) Adult patients 21 years or older
- 2) Participant of PR-COAS cohort that completed the last interview (12-month-follow-up) and authorized to be contacted for further studies.
- 3) Having at least one chronic condition (excluding cancer) diagnosed by a physician or healthcare provider.
- 4) Ability to attend weekly sessions (applicable to intervention group).

Exclusion criteria

- 1) Any clinical or cognitive impairment that limits the participant's ability to decide to participate in the study or complete the interviews.
- 2) Presence of a life threatening or extreme medical condition.

- 3) Planning to move out of the municipality within the next year.

**Sample size determination:** The primary goal of this study is to pilot the potential implementation of this intervention for Long COVID patients. We are therefore not powering for a definitive assessment of the difference between any two groups. However, we expect the preliminary data from this study to provide adequate pilot data from which we will be able to determine the required sample size for a larger scale study. The sample selected will provide an estimate of the effect size and thereby allow preliminary evaluation of the clinical utility associated with the intervention.

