**Sampling strategy:** Participants with Long-COVID and chronic diseases that agree to participate in the intervention will be allocated into one of the study intervention groups that will participate in the “Tomando Control de su Salud” workshops. Those not interested in participating in the intervention will receive general information about chronic disease management available at the CDC website in Spanish, by email, regular postal mail or in person, in addition to their regular health care and will be asked to answer the post questionnaires approximately 3 months after the last interview of the PR-COAS cohort. With an estimated participation rate of about 25 – 30% we expect to identify between 20-25 participants with Long-COVID with at least one-chronic condition. We estimate that about half will be interested in receiving the intervention; therefore, we expect to have about 20-25 participants in the intervention arm divided into two or three workshops of 8 – 12 participants based on the number of patients recruited and about 30-40 participants in the general care group. Figure 2 summarizes the expected recruitment and procedures.

**Proposed intervention:** “Tomando control de su salud” (Spanish Chronic Disease Self-Management)  is a culturally appropriate program developed in Spanish to support Hispanics

patients to build confidence in their ability to manage their health. This intervention was developed by Lorig et al. at Stanford University and has been widely used by the Puerto Rico Department of Health since it is recommended by the CDC as an evidenced-based intervention for chronic disease management.

[figure not shown]

Figure 2: Summary of study recruitment and procedures, PR COAS\_TCS

The intervention consists of small group workshops with 8 to 15 participants lead by two certified trainers, offered virtually or face-to-face (at the EHSRC Office of Clinical and Community Health Research located at the Hospital UPR in Carolina) for 2 1/2 hours once per week for six-week period open to Spanish-speakers with any physical or mental chronic condition or multiple chronic conditions. As part of the intervention, a pre and post TCS assessment will be collected.

Topics included in the training are:

- 1) Healthy eating
- 2) Appropriate exercise for maintaining and improving strength, flexibility, and endurance
- 3) Managing depression
- 4) Appropriate use of medications

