**Data analysis:** Since this is a pilot study the primary focus of the statistical analysis of this study is estimation (effect sizes and associated uncertainty). We will conduct pre- and post-intervention analysis among participants of the intervention group and between group comparisons with intervention and non- intervention groups. Descriptive analyses will be done using frequency distribution and contingency tables for categorical data. Continuous variables will be reported using mean, median, standard deviation, inter-quartile range and range. Chi-square or Fisher's exact test will be done to assess differences in sociodemographic or health indicators between the groups and to compare the independent domains of the quality-of-life scale among patients in the intervention or non-intervention group. To evaluate changes in quality of life before and after the intervention, estimates and 95% confidence intervals will be generated based on the change scores, i.e., using paired data with each subject acting as their own control. Estimates and confidence intervals will be provided for both the individual group changes as well as the difference in change between each pair of groups. We will perform Wilcoxon/Mann-Whitney U-tests (non-parametric) comparing the change scores in each group with each other. These Wilcoxon tests will be performed in addition to a Kruskal-Wallis test (non-parametric ANOVA) in order to test for an overall group effect. The Wilcoxon paired sample test will be used for ordinal data and the Mc Nemar test for significant changes will be used to evaluate dichotomous data. All analyses will be conducted using Stata version 11(Stata Corporation, College Station, Texas, USA).

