**TABLE 2: PROPOSED TIMELINE**

		9 - Months								
Proposed Activities		1	2	3	4	5	6	7	8	9
Intervention for Long-COVID – chronic disease self-management	Training or recruitment of trainers for “Tomando Control de su Salud” intervention	X	X							
	Submission and approval of IRB		X	X						
	Participant selection and group allocation				X	X	X			
	Intervention workshops (8 – 12 participants)							X	X	
	3-month follow-up interview								X	X
	Data analysis and dissemination							X	X	X

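### People who agree to TCS but never start, or stop early, have no clear follow-up date and no stated analysis group

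*Combined protocol and SAP*

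**What the plan says.** The Study design paragraph declares the design openly: "We propose to conduct a pilot non-randomized-controlled trial to evaluate the impact of" the programme. Recruitment takes place at one contact: "We will invite patients from our cohort study during the 12-month follow-up call". That same interview is the study baseline.

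Under Sampling strategy, arms follow the person's answer. Participants "that agree to participate in the intervention will be allocated into one of the study intervention groups", while "Those not interested in participating in the intervention will receive general information about chronic disease management available at the CDC website in Spanish" and form the comparison group. One inclusion criterion is specific to an arm: "Ability to attend weekly sessions (applicable to intervention group").

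Table 2 places "Participant selection and group allocation" in months 4 to 6 and "Intervention workshops (8 – 12 participants") in months 7 and 8.

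Follow-up is dated in three ways:
- The Outcome measures section sets the intervention interview a month after TCS has been completed, and the control interview about three months after the final cohort interview.
- The Consent process paragraph counts the intervention month from the end of the workshop.
- Specific Aim 2 (Behavior level) mentions interviews 3 to 6 months after the programme is implemented.

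None of these mentions people who agreed and did not attend.

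The Data analysis section announces "between group comparisons with intervention and non- intervention groups", based on change scores. It defines no analysis set (as agreed, as started or as completed) and plans no adjustment.

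**The concern.** An agreement step and an allocation step both come before treatment, but nothing makes either binding for the analysis. The wait between agreeing and the first session is long enough for health, work or motivation to change, so some agreers can be expected not to start and others to stop early.

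These people have no clear place in the plan. If their interview depends on completing TCS, they leave the data and the intervention arm becomes a completers' arm. If they are judged unable to attend, they fail a criterion that binds only the intervention arm and still satisfy those that apply to controls. Either handling lets events after baseline decide who is compared with whom. Adjustment for baseline variables would not fully remove that, and none is planned.

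Two outputs of the pilot are at stake. Under Sample size determination, the effect estimate is meant to inform the size of a larger study, so an inflated estimate would make that study too small. And the share of agreers who actually start is itself a main result for a pilot of implementation; dropping or reclassifying non-starters would hide it.

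**Working it through.** **Timing.** Let month k run from k−1 to k months elapsed, and assume that people are invited during the selection months of Table 2.
- Earliest agreement: start of month 4, 3 months elapsed.
- Workshops open: start of month 7, 6 months elapsed. Longest wait: 6 − 3 = 3.0 months. Shortest: 0.
- Latest start of a six-week course that still ends in month 8: six weeks is 6 / (52.18/12) = 1.38 months, so 8 − 1.38 = 6.62. The longest wait to a course start is then 6.62 − 3 = about 3.6 months.
- A control interviewed at the start of month 4 is due at about 3 + 3 = 6 months, just as the workshops open. An agreer of the same date who then withdraws has reached the control interview date without having had a session.

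**Following one person through the rules.** Someone agrees, is placed in a workshop and never attends.
- Outcome measures: TCS is not completed, so no interview date arises.
- Consent process: an interview a month after the workshop ends could be applied, but the text describes people who attended.
- Sampling strategy: the control group is those not interested. A person who agreed does not plainly fit.
- Inclusion criteria: inability to attend disqualifies from the intervention arm only.
- Data analysis: no rule.

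The most literal result is no follow-up. Classification as a control is possible but not prescribed. An early stopper also fails to complete, so the same interview rule leaves that person out.

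**Size.** The plan gives no non-starting rate, no SD and no effect size, so what follows is an illustration. Assumptions: 22 agree and 35 decline (inside the stated 20–25 and 30–40, taken at face value); true effect zero; a share f in both arms has a setback after baseline and changes by d = 0.5 SD less than the rest; every affected agreer fails to start.

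- As agreed: both arms average −d·f, so the difference is 0.
- Non-starters dropped: 0 − (−d·f) = d·f.
- Non-starters counted as controls: the control mean is −d·(35f + 22f)/(35 + 22f), so the difference is d·57f/(35 + 22f).

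| f | As agreed | Dropped | Counted as controls |
|---|---|---|---|
| 10% | 0 | +0.05 | 0.5 × 5.7/37.2 = +0.08 |
| 20% | 0 | +0.10 | 0.5 × 11.4/39.4 = +0.14 |
| 30% | 0 | +0.15 | 0.5 × 17.1/41.6 = +0.21 |

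With d from 0.3 to 0.8 SD and f from 10% to 30%, dropping gives 0.3 × 0.1 = 0.03 to 0.8 × 0.3 = 0.24 SD. Counting as controls gives 0.3 × 5.7/37.2 = 0.05 to 0.8 × 17.1/41.6 = 0.33 SD. If non-starters do better than the rest, d is negative and every sign reverses.

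**Against the precision of the study.** With a change-score SD of 1, the standard error is √(1/22 + 1/35) = 0.27 and the 95% half-width is 1.96 × 0.27 = 0.53 SD. In the table, the distortion runs from 0.05/0.53 = 9% to 0.21/0.53 = about 40% of that half-width.

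**The case against.** The strongest reply is that the plan does have an order: one invitation, agreement, allocation in months 4 to 6, then workshops. That stands. A reader might infer that arm membership floats with current interest, or that never-starters are sent to the control arm. The documents do not support either inference. Allocation is scheduled before treatment, and no section moves an agreer to general care. A reader might also infer that decliners later join the workshops; nothing in the plan provides for that.

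Second, the benefit of analysing as agreed depends on setbacks occurring in both arms. Suppose instead that the people who do worse are found only among agreers. Then the as-agreed difference is −0.05/−0.10/−0.15 SD, dropping non-starters gives 0, and counting them as controls gives 0.5 × 22f/(35 + 22f) = +0.03/+0.06/+0.08 SD. The as-agreed analysis is then furthest from the truth. This arithmetic is right. But that scenario is a difference in prognosis between the self-selected arms, and no choice of analysis set reliably repairs it. Events that strike people while they wait have no evident reason to spare decliners.

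Third, the direction is assumed. People may withdraw because they feel well, so the bias need not favour TCS. That also stands.

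Fourth, this is a pilot without power claims, and the distortion is smaller than the sampling error. True, but the Data analysis section makes estimation its primary focus, and a wide interval does not correct a shifted centre.

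Finally, Figure 2, which summarises recruitment and procedures, was not available in the text reviewed and may say more about allocation. Virtual delivery may also keep non-starting low.

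**Conclusion.** The gap is real and narrow. The plan does not say that agreement or allocation defines the analysis group. Its main follow-up rule for the intervention arm depends on completing TCS, and its three datings of that interview do not agree. Followed literally, it compares completers with decliners. It also leaves room to count agreers who cannot attend as controls, without prescribing it.

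Under the stated assumptions the distortion is about 0.05 to 0.21 SD, against a 95% half-width of about 0.53 SD. The non-starting rates, the 0.5 SD deficit and its equal occurrence in both arms are assumptions; only the missing rule and the wait of up to about three months come from the documents. Neither the size nor the direction of the bias can be stated as fact. The point is worth correcting before the first invitation and does not call the pilot design into question. It is separate from the self-selection at invitation, which the plan acknowledges by calling the trial non-randomized and which this correction does not remove.

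**What to change.** - **Sampling strategy:** state that each person's arm is fixed by the agreement or refusal documented at consent, and does not change with later attendance.
- **Outcome measures:** interview everyone who agreed, including non-starters and early stoppers, on a date that does not depend on completing TCS, for example one month after the end of the workshop to which they were assigned. Bring the Consent process paragraph and Specific Aim 2 into line.
- **Data analysis:** use the fixed arm for the main between-group comparison, report how many agreers never started, and show the as-attended comparison only as a sensitivity analysis.
- **Attendance:** take sessions attended from workshop logs. Form 2 asks about attendance, but as an end-of-programme form it will miss people who never start.

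The cost is a few sentences, one REDCap field and a few extra interviews. If the programme works, keeping non-starters in the TCS arm will dilute its estimate somewhat. The sensitivity analysis shows how far the result depends on attendance.

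### The plan does not provide for comparing those who enrol with eligible invitees who decline both arms, although the 12-month cohort interview should already hold baseline data on both

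*Combined protocol and SAP*

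**What the plan says.** Under Participant selection, the protocol states "We will invite patients from our cohort study during the 12-month follow-up call". Completing that interview and authorising further contact are inclusion criteria. The section on outcome measures makes the same interview the study baseline and lists its content: self-care, health-care use, vaccination, lifestyle and health-related quality of life (HRQoL).

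The Sampling strategy paragraph gives the expected yield in four steps:
- the rate: "With an estimated participation rate of about 25 – 30" per cent, with no denominator named;
- the number this yields: "we expect to identify between 20-25 participants with Long-COVID with at least one-chronic condition";
- the share taking the workshop: "We estimate that about half will be interested in receiving the intervention";
- the size of each arm: "we expect to have about 20-25 participants in the intervention arm" and, for the comparison group, "about 30-40 participants in the general care group".

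People who do not want the workshop but answer the later questionnaires form the general care group.

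The Data analysis section plans pre-post analysis in the intervention group and "between group comparisons with intervention and non- intervention groups". Tests on sociodemographic and health indicators are also between those groups. No visible section plans a count of people invited or declining, or a comparison of enrolled with non-enrolled people. Under Sample size determination, the purpose is stated as "The primary goal of this study is to pilot the potential implementation of this intervention for Long COVID patients", with the results feeding the design of a larger study.

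**The concern.** Selection operates twice: into the study, and then, by the participant's own interest and ability to attend weekly sessions, into the workshop. The planned group comparisons bear on the second step only. If those who enrol are better or worse off than those who decline both parts, then the changes, the between-group difference and the uptake figure carried to the larger study all describe a selected group, and the planned analysis would not reveal it.

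Aim 1 is worded for patients living with Long COVID in Puerto Rico. For a pilot of implementation, how many people take up the programme and how they differ from those who do not are results in their own right. Here the data needed to describe that should already be held, because the baseline is collected in the parent cohort rather than after enrolment.

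**Working it through.** **1. The plan's own counts (Sampling strategy).**
- Half of 20-25 identified = 10 to 12.5, not the 20-25 given for the intervention arm.
- Arms: 20 + 30 = 50 and 25 + 40 = 65, not 20-25.

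The plan's figures are therefore not reproduced. The Background gives three possible denominators, all preliminary cohort figures:

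| Denominator | × 0.25 | × 0.30 | Half of that |
|---|---|---|---|
| 191 (Long COVID) | 48 | 57 | 24-29 |
| 256 (infected at least four weeks earlier) | 64 | 77 | 32-38 |
| 261 (recruited) | 65 | 78 | 33-39 |

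None matches the stated ranges at both ends.

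**2. Who would be outside the trial, by reading.** Number invited = count ÷ rate. The low count is paired with 0.30 and the high count with 0.25.
- *Reading A: 50-65 enrol at 25-30% of those invited.* Invited: 50/0.30 = 167; 65/0.25 = 260. Not enrolled: 167 − 50 = 117; 260 − 65 = 195.
- *Reading B: 20-25 enrol in all.* Invited: 20/0.30 = 67; 25/0.25 = 100. Not enrolled: 67 − 20 = 47; 100 − 25 = 75.
- *Reading C: the rate is workshop uptake, giving the 20-25 in the intervention arm.* Invited 67-100, of whom 50-65 are in one arm or the other. Outside: 67 − 50 = 17; 100 − 65 = 35.

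The numbers invited are derived assumptions; the documents give none. The 260 in reading A is almost the whole recruited cohort of 261, before the eligibility criteria are applied, so the upper end of that reading is generous.

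**3. Precision of an enrolled-versus-not-enrolled comparison.** The 95% half-width of a standardised difference is 1.96 × √(1/n₁ + 1/n₀).

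| Reading | n₁, n₀ | Half-width (SD) |
|---|---|---|
| A | 50, 117 | 0.33 |
| A | 65, 195 | 0.28 |
| B | 20, 47 | 0.52 |
| B | 25, 75 | 0.45 |
| C | 50, 17 | 0.55 |
| C | 65, 35 | 0.41 |

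**4. Reach of the workshop under reading A.** 20/167 = 12% and 25/260 = 10% of those invited. The plan's statement that about half want the workshop would instead give 0.25 × 0.5 = 12.5% to 0.30 × 0.5 = 15%. The gap is another effect of the unreconciled counts.

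**The case against.** The strongest reply is that this is an unpowered pilot focused on estimation, that eligibility criteria and descriptive tables will describe the enrolled sample, and that a plan's silence does not discard data held by a separate cohort study. All of that is fair, and it limits the point to a gap in reporting. Figure 2, not shown here, may also give recruitment counts; its absence is not held against the plan.

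Three stronger readings are tempting and not supported:
- *That 70-75% of invited patients will be lost.* This is the complement of the stated rate (1 − 0.30 and 1 − 0.25) only if the rate is per person invited, which is not stated. Those who decline only the workshop and answer the questionnaires are the control group. Under reading C most of the 70-75% would be that group.
- *That nobody can say to whom the results apply.* The enrolled sample will be described. What is missing is its relation to those invited.
- *That selection into the trial would be better estimated than any planned between-group contrast.* A cross-sectional difference between arms has a half-width of 0.57 SD (20 v 30) to 0.50 SD (25 v 40). The plan, however, analyses change scores, which multiplies these by √(2(1 − r)), in baseline-SD units with equal SDs at both times. The pre-post correlation r is not given. At r = 0.5 the half-width is 0.50-0.57; at 0.7, 0.39-0.44; at 0.85, 0.27-0.31. The claim fails for high r, and its advantage largely disappears under readings B and C.

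Two qualifications on the data also stand. That decliners have a complete interview is inferred from the timing of the invitation and the inclusion criterion, and the workshop's own initial and final forms exist only for attenders. Table 1 labels its HRQoL row as follow-up, although its title and the outcome section cover baseline too. Permission to use decliners' cohort data is not documented.

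**Conclusion.** The point holds as a cheap and worthwhile addition. As written, the plan cannot show how far the enrolled sample represents the eligible people invited, because it analyses only the two enrolled groups and does not provide for recording the outcome of invitations. The comparison should be possible from data already held. Its precision is about ±0.28 to ±0.33 SD if 50-65 enrol at 25-30% of those invited, and about ±0.41 to ±0.55 SD on the other readings. It could therefore show a marked difference, but would not exclude a moderate one.

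This rests on two assumptions: that eligible decliners completed the 12-month interview, and that their data may be used. The conflict between 20-25 identified and 50-65 across arms stands on the plan's own figures and needs neither.

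**What to change.** 1. In Sampling strategy, state the denominator of the participation rate and reconcile the 20-25, the half, and the 50-65.
2. At the 12-month call, record the numbers invited, eligible, declining both parts, choosing general care and choosing the workshop. Link this status to the cohort record before identifiers are removed at the end of data cleaning.
3. In Data analysis, add a descriptive table with three groups: workshop, general care, and eligible invited but not enrolled. Take it from the 12-month interview, covering the HRQoL scales it contains, age, sex, chronic conditions, Long COVID symptoms and health-care use. Give standardised differences with 95% confidence intervals.
4. Word the conclusions on Aims 1 and 2 for people like those enrolled, in light of that table.

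I would attach no numerical trigger. A cut-off such as 0.25 SD lies below even the best half-width above (0.28), so across several variables it would often be crossed by chance. Reweighting to those invited should be exploratory at most with 20-25 workshop participants.

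The cost is one extra table and a short log at the call, with no new contact. The sponsor must also confirm that cohort consent or the IRB permits de-identified use of non-enrolled members' 12-month data.

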Our second study was designed to establish a cohort of Hispanic patients living in Puerto Rico with laboratory-confirmed COVID-19 infection to evaluate the clinical, epidemiological, and risk factors associated with the development of post-COVID-19 sequelae and its impact on the quality of life. Sociodemographic characteristics, comorbidities, vaccination status, persistent or new symptoms after acute infection, healthcare utilization, and quality of life were collected in the initial or follow-up interviews done at 3, 6, 9 and 12 months (in progress). In our preliminary results we found that of 261 patients recruited, 256 had a SARS-CoV-2 infection at least four weeks before the interview. Of these, the mean age was  $48.1 \pm 15.9$  years, 201 (78.8%) were women, and **191 (74.6%) had signs and symptoms compatible with Long-COVID**. Participants with and without Long COVID had a similar mean age, were mainly women, had similar education, and had received their third dose or booster of COVID-19 vaccine. However, participants with Long COVID had a significantly higher prevalence of tiredness, muscle pain, headaches, joint pain, and anxiety than those without Long-COVID. After adjusting for age, sex, and disease severity, **having a chronic condition was significantly associated with higher odds of Long COVID** (OR=3.38; 95% CI=1.62 – 7.04) including asthma (OR=4.78; 95% CI, 1.92 – 11.9), obesity (OR=3.42; 95% CI, 1.64 – 7.13), hypertension (OR=3.04; 95% CI, 1.33 – 6.98), and diabetes (OR=2.76; 95% CI 1.12- 6.77). In addition, we identified a significant impact in the quality of life where those patients living with Long COVID were more likely to report difficulties with daily activities (24% vs. 9%,  $p = 0.01$ ), pain or discomfort (52% vs. 17%,  $p < 0.001$ ), and anxiety or depression symptoms (37% vs. 11%,  $p < 0.001$ ).

[figure not shown]

Figure 1: Prevalence of Long-COVID Symptoms, Puerto Rico COAS

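### The expected enrolment figures do not agree: about half of 20–25 identified people is 10–12 in TCS, not the stated 20–25 in TCS plus 30–40 in general care

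*Combined protocol and SAP*

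**What the plan says.** All the enrolment figures are in Methods, Sampling strategy, in two consecutive sentences.

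- Participation: "With an estimated participation rate of about 25 – 30" per cent. The text does not say of whom.
- Yield: "we expect to identify between 20-25 participants with Long-COVID with at least one-chronic condition".
- Uptake: "We estimate that about half will be interested in receiving the intervention".
- TCS arm: "therefore, we expect to have about 20-25 participants in the intervention arm", "divided into two or three workshops of 8 – 12 participants", with the number of workshops depending on recruitment.
- Comparison group: "about 30-40 participants in the general care group". The same section forms this group from people who do not want the workshops.

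Methods, Sample size determination, gives no number. It says the pilot is not powered to compare groups and that its data will be used to size a larger study. Methods, Data analysis, makes estimation of effect sizes and their uncertainty the primary focus, and plans confidence intervals for the difference in change between each pair of groups. Specific Aim 2 (the learning and behavior levels) refers to one control group and two intervention groups. Methods, Participant selection, invites cohort members with Long COVID or with chronic disease, and its inclusion criteria do not list Long COVID.

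**The concern.** The plan presents the arm sizes as following from the number identified and the uptake share, but they do not. Half of 20–25 cannot be 20–25, and a comparison group made up of the other half cannot be 30–40.

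A reader therefore cannot tell whether the plan is for 20–25 people or for 50–65. In a pilot meant to estimate effects and size a later study, that choice determines how wide the intervals will be. It also determines whether there are enough people for more than one workshop, and so for the two intervention groups named in Specific Aim 2.

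**Working it through.** **Inputs** (all from Sampling strategy): identified 20–25; uptake about one half; TCS arm 20–25; general care 30–40; workshops two or three, of 8–12 people; participation rate 25–30%, base not stated.

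**1. The plan's own figure.** TCS = identified × uptake; general care = the remainder.

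| Uptake | TCS | General care |
|---|---|---|
| 0.5 | 10–12.5 | 10–12.5 |
| 0.4 | 8–10 | 12–15 |
| 0.6 | 12–15 | 8–10 |
| Stated | 20–25 | 30–40 |

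The stated arms are not reproduced at either end of either range, even when one half is stretched to 40–60%. At one half, the stated TCS arm is twice the derived one (20/10 = 25/12.5 = 2.0). The stated general care group is about three times the derived one (30/10 = 3.0; 40/12.5 = 3.2).

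**2. Total.** 20 + 30 = 50 and 25 + 40 = 65, against 20–25 identified.

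**3. Working backwards from the TCS arm.** At one half, 20–25 in TCS needs 20/0.5 = 40 to 25/0.5 = 50 identified. That leaves 20–25 for general care, not 30–40.

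**4. Reading 25–30% as uptake of TCS.** The invited pool would be 20/0.30 = 67 to 25/0.25 = 100, with about 47–75 decliners (66.7 − 20 = 46.7; 100 − 25 = 75). That could supply 30–40 in general care. It contradicts both the one-half uptake and the statement that 20–25 are identified.

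**5. Workshops.** Two workshops of at least 8 need 16 people. An arm of 10–12 fills one; so does an arm of 15, the most that 60% uptake of 25 would give.

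**6. Precision.** For the between-group difference in mean change, in units of the SD of change:

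half-width = t(0.975, n1 + n2 − 2) × √(1/n1 + 1/n2)

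| Arms (TCS, general care) | Half-width (SD) |
|---|---|
| 20, 30 (stated, low) | 0.58 |
| 25, 40 (stated, high) | 0.51 |
| 10, 10 (total of 20) | 0.94 |
| 13, 12 (total of 25) | 0.83 |

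If 20–25 is the total, the interval is about 1.6 times as wide (0.94/0.58 = 1.62; 0.83/0.51 = 1.63).

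**The case against.** The strongest reply is that these are approximate accrual expectations in a pilot that is openly not powered. No power calculation, stopping rule or success criterion uses them, and the number of workshops adapts to recruitment. General care might also draw on a wider pool, because the invitation covers chronic disease with or without Long COVID. Figure 2, which summarises expected recruitment, could not be seen.

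Much of this lowers the severity, but it does not remove the contradiction. Rounding does not cover a twofold gap in one arm and a threefold gap in the other. A wider pool could explain a larger general care group and weakens the comparison of 50–65 with 20–25. It does not help the TCS arm, because Sampling strategy fills the workshops with people who have both Long COVID and chronic disease. Whatever Figure 2 shows, it could not make these two sentences agree.

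A reader might infer four stronger things that the documents do not support.

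- **That the workshop numbers fail at the ends of the TCS range.** They do not: 20 people in two workshops is 10 each, and 25 in three is 8.3 each.
- **That the preliminary cohort counts prove the 20–25 wrong.** The Background reports that "of 261 patients recruited, 256 had a SARS-CoV-2 infection at least four weeks before the interview", and that 191 of them had Long COVID. Neither 256 nor 191 is the eligible pool. Eligibility also requires age 21 or over, a completed 12-month interview, permission for contact and a diagnosed non-cancer chronic condition. A pool of about 67–100 would yield 20–25 at the stated rate, and nothing in the text excludes it. For the same reason, replacement figures should not be built on 191.
- **That the number identified is simply a drafting slip.** This is plausible, since two intervention groups fit the stated TCS arm better, but the documents do not say so.
- **That the smaller study could give no usable between-group estimate.** The plan sets no precision threshold; the supportable statement is that the estimate would be much less precise.

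**Conclusion.** The inconsistency is real and lies within the plan's own text. With 20–25 identified and about half choosing TCS, the arm is about 10–12, against 20–25 stated. No reading tried reconciles all the figures. This is the only planned sample size in the readable text, so it should be fixed. It does not undermine an unpowered pilot.

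The consequence is uncertainty over precision: a half-width of 0.51–0.58 SD at the stated arms, or 0.83–0.94 SD if 20–25 is the total. These values assume an equal SD of change in both arms, complete follow-up, no clustering by workshop and no covariate adjustment. The second range also assumes that general care contains only the remaining half of those identified; a wider general care group would narrow it. The point about two intervention groups assumes that each is at least one workshop of the planned size, which the documents do not spell out.

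**What to change.** Rewrite the enrolment statement in Sampling strategy as one chain:

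- eligible base × participation rate = total enrolled;
- total enrolled × share choosing TCS = TCS arm, with the remainder in general care;
- TCS arm ÷ 8–12 = number of workshops.

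The authors should name the denominator of the 25–30% rate and correct either the number identified or the arm sizes to match. Only they hold the eligible count, so no replacement figures are offered here. They should state whether general care may include people without Long COVID; if it may, that group's source and expected size need a separate line. They should check that the result agrees with Figure 2 and with the two intervention groups in Specific Aim 2, and add the expected 95% confidence interval half-width for the difference in change.

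The cost is protocol wording only. The downside is that some stated figures, whether arm size, number of workshops or precision, may become less favourable.
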